AUC _{0-α}	area under the concentration-time curve from time zero to infinity
β -hCG	beta human chorionic gonadotrophin
BID	twice daily
BP	blood pressure
BUN	blood urea nitrogen
CARLOS	cartilage loss score
CFR	Code of Federal Regulations
Cmax	maximum plasma concentration
COVID-19	coronavirus disease 2019
CRF	case report form
CRP	C-reactive protein
CSR	clinical study report
DAS	Disease Activity Score
DAS28-CRP	Disease Activity Score using 28 joint count-C-reactive protein
DMARD	disease-modifying antirheumatic drugs
ECG	electrocardiogram
eGFR	estimated glomerular filtration rate
FSH	follicle-stimulating hormone
GCP	Good Clinical Practice

HAQ-DI	Health Assessment Questionnaire – Disability Index
HIPAA	Health Insurance Portability and Accountability Act
hsCRP	high sensitivity C-reactive protein
IB	Investigator's Brochure
IC	Inhibitory concentration
ICF	informed consent form
ICH	International Council for Harmonisation
IEC	Independent Ethics Committee
IL	interleukin
INR	international normalized ratio
IRB	Institutional Review Board
ITT	intent-to-treat
JAK	Janus kinase
LPS	lipopolysaccharide
MAPK	mitogen-activated protein kinase
MedDRA	Medical Dictionary for Regulatory Activities
MK2	MAPK-activated protein kinase 2
MRI	magnetic resonance imaging
MTX	methotrexate
NOMID	neonatal-onset multisystem inflammatory disease
NSAIDS	non-steroidal anti-inflammatory drugs
PD	pharmacodynamic(s)
PK	pharmacokinetic(s)
PRAK	p38 α -related/activated protein kinase
QTL	quality tolerance limits
RA	rheumatoid arthritis
RAMRIS	Rheumatoid Arthritis Magnetic Resonance Imaging Score
RT-PCR	reverse transcription polymerase chain reaction
SAE	serious adverse event
SARS-CoV-2	severe acute respiratory syndrome coronavirus 2
SAP	statistical analysis plan

$t_{1/2}$	half-life
TB	tuberculosis
TEAE	treatment-emergent adverse event
T_{max}	time to maximum plasma concentration
TMF	trial master file
TNF α	tumor necrosis factor- α
ULN	upper limit of normal
VAS	visual analog scale
WBC	white blood cell

1 INTRODUCTION AND RATIONALE

1.1 Background

1.1.1 Background

Aclaris Therapeutics, Inc. is developing ATI-450, an orally available, small molecule inhibitor of the p38 α mitogen-activated protein kinase (MAPK)/MAPK-activated protein kinase 2 (MK2) inflammatory signaling pathway. This pathway drives the expression of multiple cytokines, chemokines, matrix metalloproteases, and other inflammatory signals. Key inflammatory cytokines driven by this pathway include tumor necrosis factor- α (TNF- α), interleukin-1 α and β (IL-1 α and β), and interleukin-6 (IL-6).

ATI-450 has a novel mechanism of action. It targets the high affinity docking interaction between p38 α MAPK and MK2. Upon binding to the interface created upon formation of this bimolecular complex, ATI-450 blocks MK2 phosphorylation by p38MAPK and thereby the downstream MK2-mediated inflammatory drive. ATI-450 shows low potency for inhibition of p38 α phosphorylation/activation of alternate substrates and is selective across the human kinase.

Aclaris Therapeutics, Inc is developing ATI-450 for potential treatment of inflammatory disorders.

A high-contrast, black and white image showing a series of horizontal bands. The top band is dark with a small white rectangular cutout on the left. Below it is a white band with a dark rectangular cutout on the left. The third band is dark with a large white rectangular cutout in the center. The fourth band is dark with a small white rectangular cutout on the left. The fifth band is dark with a large white rectangular cutout in the center. The sixth band is dark with a small white rectangular cutout on the left. The bottom band is dark with a large white rectangular cutout in the center. The image has a high-contrast, binary appearance, suggesting it might be a scan of a document or a specific type of film strip.

ATI-450-related adverse effects noted in either species. ATI-450-related findings in rats

A series of five horizontal black bars of increasing length, each ending in a white step-like pattern. The bars are positioned vertically, with the first bar at the top and the fifth bar at the bottom. The length of the bars increases from left to right. Each bar ends in a white step-like pattern, with the first bar having a single step and the fifth bar having a more complex, multi-step pattern.

1.2 Study Rationale

The assessment of 12-weeks of ATI-450 exposure in patients with RA will provide important data to initially describe the safety and tolerability of ATI-450 in a relevant patient population.

The p38 MAPK pathway offers great potential in the treatment of inflammatory diseases such as RA. Unfortunately, this potential has not been realized in clinical studies where it has been hypothesized that the lack of efficacy resulted from the development of tachyphylaxis.^{1, 2, 3}

The tachyphylaxis hypothesis has been supported by the consistent observation in the studies cited above, that C-reactive protein (CRP) showed an initial rapid reduction, followed by a return to baseline within 4 to 8 weeks. It is thought this may be a result of p38 MAPK inhibitors inhibiting anti-inflammatory downstream substrates in addition to proinflammatory substrates.

By targeting MK2, which is downstream from p38, it is believed that ATI-450 can inhibit the inflammatory pathways without a significant impact on anti-inflammatory pathways, which could lead to the avoidance of tachyphylaxis. This hypothesis is supported by pre-clinical models.

The consistent pattern of CRP tachyphylaxis with p38 inhibition provides an efficient model to test the potential of MK2 inhibition to avoid tachyphylaxis, i.e., if a reduction in CRP is achieved and maintained over 12 weeks, MK2 inhibition will have been shown to have a PD profile that is distinct from p38 inhibition and one that could offer potential for efficacy in RA. This study will assess the CRP profile.

This study is being conducted to determine the safety, tolerability, PK, PD and preliminary efficacy of ATI-450 in combination with MTX in patients with moderate to severe RA. The results of this study may benefit patients with RA.

2 STUDY OBJECTIVES AND ENDPOINTS

The objectives and endpoints for this study are provided in [Table 2](#) below.

Table 2 Study Objectives and Endpoints

Objectives		Endpoints
Primary	
 To assess the safety and tolerability of ATI-450 plus MTX in patients with moderate to severe RA 	
 Number and percent of AEs and SAEs; mean change from baseline in laboratory values, vital signs, and ECGs
Secondary	
 To assess the PD of ATI-450 plus MTX in patients with moderate to severe RA 	
 Median percent change from baseline in high sensitivity C-reactive protein (hsCRP) levels over time Mean change from baseline in Disease Activity Score using 28 joint count-C-reactive protein (DAS28-CRP) over time Proportion of patients with DAS28-CRP below 2.6 Mean change from baseline in Rheumatoid Arthritis Magnetic Resonance Imaging Score (RAMRIS) Hand-Wrist assessments of synovitis or osteitis at Week 12 Proportion of patients with American College of Rheumatology (ACR)20/50/70 over time
	
 To assess the PK of ATI-450 in patients with moderate to severe RA who are receiving concomitant MTX 	
 ATI-450 concentrations at trough and 2 hours post-dose
Exploratory	
 To assess the PD of ATI-450 plus MTX in patients with moderate to severe RA 	
 Mean change from baseline in endogenous cytokine levels (e.g. TNF-α, IL-1β, IL-6, IL-8, IFNγ, IL-17, IL-18, IL-10, IL-1α, and IL-1RA) Mean change from pre-dose in ex vivo stimulated cytokine levels (e.g. TNF-α, IL-1β, IL-6, IL-8, IFNγ, IL-17, IL-18, IL-10, IL-1RA and IL-1α) Ex vivo stimulated phosphoprotein modulation

		
• Mean change from baseline in the cartilage loss score (CARLOS) Hand-Wrist magnetic resonance imaging (MRI) assessment of cartilage loss
--	--	-------------------------------------------------------------------------------------------------------------------------------------------------------------------------------------------

3 STUDY PLAN

3.1 Overall Study Design and Plan

The study visit schedule and planned assessments at each visit are detailed in [Table 1](#).

This is a Phase 2a, randomized, investigator- and patient-blind, sponsor-unblinded, parallel group, placebo-controlled study to investigate the safety, tolerability, PK, and PD of ATI-450 plus MTX versus MTX alone in patients with moderate to severe RA.

Approximately 25 patients are planned to be enrolled with the expectation that at least 15 patients will complete the 12-weeks of treatment. The study will consist of an up to 28-day screening period, a 12-week treatment period, and a 4-week follow-up period. The total duration of the study for patients remaining in the study until their final follow-up assessment will be up to 20 weeks.

The investigator will obtain signed informed consent from the patient before any study procedures are performed. For further details regarding the informed consent process, see [Section 9.3](#).

During the screening period each patient will be required to have all assessments performed as outlined in the Schedule of Assessments ([Table 1](#)). The MRI is not to be performed until the site obtains the results of the patient's hsCRP level to ensure that this assessment meets entry criteria prior to performing the MRI. The patient will have the RAMRIS Hand-Wrist assessment performed at their local institution and evaluated by a central radiology review team to determine if they meet the radiological inclusion criteria. Results for all of the screening assessments must be available at the time patient eligibility is reconfirmed prior to randomization and dosing.

Patients whose eligibility is confirmed at baseline will be randomized in a 3:1 ratio to receive either ATI-450 tablets (50 mg BID) plus MTX, or matching placebo tablets plus MTX. Study medications will be administered orally for 12 weeks. Patients will be required to remain on a stable dose of MTX (7.5 mg to 25 mg/week) and a stable dose of folic or folinic acid (≥ 5 mg/week) for the duration of the study.

Patients will attend clinic visits on Days 7, 14, 28, 42, 56, and 84 (± 1 day) for safety, efficacy, PK, and PD assessments. The morning dose of study medication will be administered in the clinic on each study visit day.

After 4 weeks of treatment (Day 28), each patient's safety data (e.g., AEs, laboratory values, vital signs, ECGs) will be reviewed by the Aclaris medical monitor and the Aclaris safety physician to ensure that the patient is tolerating the treatment regimen and is deemed suitable to continue treatment for the next 8 weeks. This review is described in more detail in the study-specific safety management plan.

End of study assessments will be conducted on Day 84 (Week 12). A safety follow-up visit will be conducted 30 days (+7 days) after the last dose of study medication.

The study is randomized and blinded to the investigator, patient, site personnel and Aclaris clinical monitors involved in site and patient monitoring with regard to ATI-450 and placebo to prevent bias in treatment allocation and in the assessment of treatment effect. See [Section 6.2](#) for details on access to the treatment codes in the event of emergency unblinding. The Aclaris statistician, medical and safety monitor will be unblinded to each patient's treatment assignment.

3.2 Discussion of Study Design

The study is designed to assess the safety and tolerability of ATI-450 in a relevant patient population (i.e., patients with RA).

The study will also describe the PK and PD of ATI-450 in a relevant disease. The efficacy hypothesis to be explored is described in [Section 1.2](#) and provides justification for recruiting a population with active RA and elevated hsCRP.

Investigator and patient blinding will maintain integrity for assessments of safety and AEs. The 3:1 randomization schedule will maximize the number of patients receiving active drug to allow for a more robust assessment for the change from baseline in hsCRP.

The 12-week treatment period is sufficient to explore the tachyphylaxis signal (observed within that timeframe by p38 MAPK inhibitors). Treatment of all patients with MTX ensures that all patients will receive active treatment for their RA throughout the study.

3.3 End of Study

A patient is considered to have completed the study if he/she has completed all study visits. The end of the study is defined as the date of the last visit or date of last procedure of the last patient in the study.

4 STUDY POPULATION

Prospective approval of protocol deviations to recruitment and enrollment criteria, also known as protocol waivers or exemptions, is not permitted.

4.1 Inclusion Criteria

The following inclusion criteria must be met for a patient to be eligible for inclusion in the study:

1. Able to comprehend and be willing to sign the Institutional Review Board (IRB) approved subject informed consent form (ICF) prior to the administration of any study-related procedures.
2. Diagnosis of adult-onset RA as defined by the 2010 American College of Rheumatology/European League Against Rheumatism (ACR/EULAR) classification criteria.
[REDACTED]
3. [REDACTED]
4. [REDACTED]
5. [REDACTED]
6. Patients must have definitive intra-articular synovitis or osteitis defined as a score of 1 or greater on a Hand-Wrist MRI as assessed by central imaging reader (using RAMRIS).
7. On a stable MTX dose (defined as 7.5 mg to 25 mg weekly) and a stable dose of folic or folinic acid (defined as \geq 5mg/week) for at least 4 weeks prior to the screening visit.
8. Male or non-pregnant, non-nursing female patients between 18 and 70 years of age, inclusive.
 - Female patients that are of childbearing potential must use 2 methods of highly effective contraception* - one of which must be a physical barrier for the duration of the study and for 30 days after the last dose
 - Male patients of childbearing potential with a female partner of childbearing potential must agree to use a condom plus another highly effective form of birth control for the duration of the study and for 90 days after the last dose
9. Female patients must have a negative serum pregnancy test at screening and a negative urine pregnancy test prior to dosing on Day 1.
10. Screening laboratory evaluations (hematology, chemistry, coagulation, and urinalysis) must fall within the normal range of the central laboratory's reference ranges unless the results have been determined by the investigator to not be clinically significant.
11. Willing and capable of taking appropriate coronavirus disease 2019 (COVID-19) risk mitigation precautions (e.g., wearing a mask in public, adhering to social

distancing, etc.) as recommended or required by local, state, or federal guidelines during participation in the study.

*Highly effective birth control is defined as those which result in a low failure rate (i.e., less than 1% per year) when used consistently and correctly such as implants, injectables, combined oral contraceptives, some intrauterine devices, heterosexual abstinence, or vasectomized. The requirements for highly effective birth control do not apply to female patients of nonchildbearing potential (i.e., physiologically incapable of becoming pregnant) defined as:

- Has had a complete hysterectomy greater than or equal to 3 months prior to dosing or
- Has had a bilateral oophorectomy (ovariectomy) or
- Has had a bilateral tubal ligation or fallopian tube inserts or
- Is postmenopausal (i.e., cessation of regular menses for at least 12 consecutive months with no alternative pathological or physiological cause and have a serum follicle-stimulating hormone (FSH) level >40 mIU/mL) or
- Medically documented ovarian failure

4.2 Exclusion Criteria

A patient who meets any of the following exclusion criteria will not be eligible for inclusion in the study:

1. Patient has a current acute or chronic immunoinflammatory disease other than RA which may impact the course or assessment of RA.
2. Patient has an uncontrolled non-immunoinflammatory disease that may place the patient at increased risk during the study or impact the interpretation of results.
3. History or evidence of active or latent tuberculosis (TB).
4. Known hypersensitivity to MTX or ATI-450.
5. Patient has either a history of alcoholism/current alcoholic, alcoholic liver disease, or other chronic liver disease.
6. Active infection requiring treatment with antibiotics.
7. Positive for HIV, hepatitis B or C. Patients with serologic evidence of hepatitis B vaccination (hepatitis B surface antibody without the presence of hepatitis B surface antigen) will be allowed to participate.
8. Tests performed at a central laboratory at screening that meet any of the criteria below (out of range labs may be rechecked one time, after consultation with sponsor or designee, before patient is considered a screen failure):
 - White blood cell (WBC) count $<3.0 \times 10^3$ cells/mm³

- ANC $<1.5 \times 10^3$ cells/mm³
- Lymphocyte count $<0.5 \times 10^3$ cells/mm³
- Platelet count $<100 \times 10^3$ cells/mm³
- Hemoglobin <10 g/dL
- Aspartate aminotransferase (AST) or alanine aminotransferase (ALT) $\geq 1.5 \times$ upper limit of normal (ULN)
- Total bilirubin level $\geq 2 \times$ ULN unless the patient has been diagnosed with Gilberts' disease and this is clearly documented
- Estimated glomerular filtration rate (eGFR), <40 mL/min/1.73m² based on Modification of Diet and Renal Disease formula

9. Any clinically significant laboratory abnormality that would affect interpretation of study data or safety of the patient's participation in the study, per judgment of investigator.
10. Patient has clinically significant abnormal findings other than RA from physical examination conducted at screening visit (Visit 1) and at baseline visit (Visit 2) that may affect the interpretation of study data or the safety of the patient's participation in the study, per the judgment of the investigator.
11. Patient has a clinically important history of a medical disorder that would compromise patient safety or data quality (per investigator's judgment).
12. Blood pressure levels (in supine position after at least 5 minutes rest): <90 mmHg or >140 mmHg for systolic blood pressure or <40 mmHg or >90 mmHg for diastolic blood pressure.
13. Has taken any of the following within the defined time period prior to screening visit:
 - Conventional synthetic disease-modifying antirheumatic drugs (DMARDs) (leflunomide, cyclosporine, azathioprine): 30 days
 - Rituximab or other B cell inhibitors: 6 months
 - Biologic DMARDs (infliximab, golimumab, adalimumab, certolizumab pegol, abatacept, and tocilizumab): 8 weeks
 - Etanercept and anakinra: 4 weeks
 - Janus kinase (JAK) inhibitors: 30 days
 - Investigational small molecules: 30 days

- Intra-articular corticosteroid injection: 30 days

14. Are currently receiving corticosteroids at doses greater than 10 mg per day of prednisone (or equivalent) or have been receiving an unstable dosing regimen of corticosteroids within 2 weeks of the screening visit.

15. Have started treatment with non-steroidal anti-inflammatory drugs (NSAIDs) or have been receiving an unstable dosing regimen of NSAIDs within 2 weeks of the screening visit.

16. Patients with history of stroke.

17. Significant cardiac disease that would affect interpretation of study data or the safety of the patient's participation in the study, per judgment of the investigator, including recent myocardial infarction or unstable angina, or heart failure with New York Heart Association Class III or IV symptoms.

18. Patients with the following screening or pre-dose ECG findings, specifically:

- Evidence of atrial fibrillation, atrial flutter, complete right or left bundle branch block, Wolff-Parkinson-White Syndrome, or other significant rhythm disturbance
- Evidence of acute ischemia
- Screening or pre-dose baseline mean QTcF >450 msec for males or >470 msec for females (use of the ECG algorithm is acceptable for this purpose)
- Personal or family history of congenital long QT syndrome or sudden death
- Any other finding that is considered clinically significant

19. Any joint procedure in past 90 days prior to screening

20. Known exposure to an individual with a confirmed, active diagnosis of COVID-19 at any time during the screening period.

21. Vaccination with a live or attenuated vaccine within 6 weeks prior to Baseline (Visit 2) or planned vaccination with these vaccines at any time during treatment or within 6 weeks following discontinuation of study medication.

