*Highly effective birth control is defined as those which result in a low failure rate (i.e., less than 1% per year) when used consistently and correctly such as implants, injectables, combined oral contraceptives, some intrauterine devices, heterosexual abstinence, or vasectomized. The requirements for highly effective birth control do not apply to female patients of nonchildbearing potential (i.e., physiologically incapable of becoming pregnant) defined as:

- Has had a complete hysterectomy greater than or equal to 3 months prior to dosing or
- Has had a bilateral oophorectomy (ovariectomy) or
- Has had a bilateral tubal ligation or fallopian tube inserts or
- Is postmenopausal (i.e., cessation of regular menses for at least 12 consecutive months with no alternative pathological or physiological cause and have a serum follicle-stimulating hormone (FSH) level >40 mIU/mL) or
- Medically documented ovarian failure

Exclusion Criteria

A patient who meets any of the following exclusion criteria will not be eligible for inclusion in the study:

1. Patient has a current acute or chronic immunoinflammatory disease other than RA which may impact the course or assessment of RA.
2. Patient has an uncontrolled non-immunoinflammatory disease that may place the patient at increased risk during the study or impact the interpretation of results.
3. History or evidence of active or latent tuberculosis.
4. Known hypersensitivity to MTX or ATI-450.
5. Patient has a history of either alcoholism/current alcoholic, alcoholic liver disease, or other chronic liver disease.
6. Active infection requiring treatment with antibiotics.
7. Positive for HIV, hepatitis B or C. Patients with serologic evidence of hepatitis B vaccination (hepatitis B surface antibody without the presence of hepatitis B surface antigen) will be allowed to participate.
8. Tests performed at a central laboratory at screening that meet any of the criteria below (out of range labs may be rechecked one time, after consultation with sponsor or designee, before patient is considered a screen failure):
 - White blood cell count $<3.0 \times 10^3$ cells/mm³
 - Absolute neutrophil count $<1.5 \times 10^3$ cells/mm³
 - Lymphocyte count $<0.5 \times 10^3$ cells/mm³
 - Platelet count $<100 \times 10^3$ cells/mm³
 - Hemoglobin <10 g/dL
 - Aspartate aminotransferase (AST) or alanine aminotransferase (ALT) $\geq 1.5 \times$ upper limit of normal (ULN)

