5.1 Demographics and Other Screening Assessments

Screening assessments that are also part of the safety assessments are described in [Section 5.3](#).

5.1.1 *Medical History*

Relevant medical history and current medical condition, including RA disease phenotype and duration as well as date of first diagnosis and previous treatments including any previous biologic or non-biologic therapy for RA will be recorded in the electronic case report form (eCRF).

At the baseline visit, inclusion/exclusion criteria will be reviewed and updated to ensure the patient remains qualified for the study. Significant findings that are observed after the patient has signed the ICF and prior to the first dose of study medication will be recorded as medical history on the eCRF. Any event observed after the patient has signed the ICF that meets the definition of a SAE will be recorded on the SAE eCRF.

5.1.2 *Demographics*

Demographic data, including year of birth/age, sex (at birth), and race, will be recorded in the eCRF.

5.1.3 *Tuberculosis Test*

An interferon-gamma release assay/QuantiFERON TB Gold test for active/latent TB will be performed at screening with analysis conducted by the sponsor's designated central laboratory. Patients with a negative test result will be eligible for the study.

In case of indeterminate results, the test may be repeated once. The patient can be included in the study if the repeat test is negative; however, if the repeat test is positive or indeterminate, the patient will be excluded from the study.

5.1.4 *Screening Clinical Laboratory Assessments*

Blood samples will be collected for clinical chemistry, coagulation, hematology, hsCRP, lipids, FSH, hepatitis B surface antigen, hepatitis B core antibody, hepatitis C antibody, and HIV-1/HIV-2. A serum pregnancy test will be performed on women of childbearing potential. All laboratory analyses will be performed by the sponsor's designated central laboratory.

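### Exclusion 7 defines hepatitis B vaccination without core antibody, so read literally its exemption also fits a resolved past infection

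*Combined protocol and SAP*

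**What the plan says.** Criterion 7 in protocol section 4.2 has two sentences. The first excludes patients who are "Positive for HIV, hepatitis B or C" and names no marker for any of the three viruses. The second lets in patients with "serologic evidence of hepatitis B vaccination (hepatitis B surface antibody without the presence of hepatitis B surface antigen". The Protocol Summary repeats the definition, "hepatitis B surface antibody without the presence of hepatitis B surface antigen", so it adds nothing that would settle the meaning.

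Section 5.1.4 lists the viral serology drawn at screening: "hepatitis B surface antigen, hepatitis B core antibody, hepatitis C antibody, and HIV-1/HIV-2". Surface antibody is not in that list. Core antibody is, but no readable text says what a positive core result means for eligibility. The only other mention of core antibody is in Appendix 1, footnote 3, as part of the work-up after a liver event.

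Section 4.4.1 lists reactivation of hepatitis B among the events that require stopping study medication. The visible part of Table 1 shows the HIV and hepatitis screen at the screening visit only.

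**The concern.** The exemption is meant for vaccinated patients, but the definition attached to it does not separate them from patients with a resolved infection. Both groups can have surface antibody and no surface antigen. The result that distinguishes them is core antibody, and the definition leaves it out. Taken at its word, the exemption therefore admits a patient with a past infection, the kind of patient in whom reactivation could occur.

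What is at stake is patient safety, which is the primary objective, and uniform application of an eligibility rule across sites. Section 4 does not permit waivers, and section 11.2 gives enrolment against key eligibility criteria as an example of an important deviation. Sites and monitors should therefore be able to tell from the criterion itself whether a given serology is eligible. The protocol names the hazard and collects the deciding result, but the exemption does not use it.

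**Working it through.** No arithmetic applies, and the plan states no figure to reproduce. The check is to apply criterion 7 to a patient who is surface antigen negative and core antibody positive on the section 5.1.4 panel. What the markers mean (core antibody reflecting infection, not vaccination) is standard serology that the protocol does not spell out; it is taken here as an assumption.

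**Step 1: surface antibody not known.** This is the default, because the listed panel does not include it. The exemption cannot be invoked, so only the first sentence applies. The patient has a positive result on a hepatitis B test that the protocol orders at screening. The natural reading is that a positive result on a listed screen excludes. Hepatitis C supports this: its only listed test is an antibody, so being positive for hepatitis C can only mean antibody positive. Outcome: excluded, by inference.

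**Step 2: surface antibody known and negative.** The exemption does not apply. The outcome is the same as in step 1.

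**Step 3: surface antibody known and positive**, for example from the medical record. The first sentence, read as in step 1, excludes. The second sentence, read by its parenthesis, admits: surface antibody is present and surface antigen is absent. The word vaccination points back towards exclusion, but the parenthesis is what defines the evidence. Here the two sentences conflict.

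**Step 4: do other entry criteria settle step 3?**
- Inclusion 10 covers hematology, chemistry, coagulation and urinalysis, not serology.
- Exclusion 5 (chronic liver disease) and exclusion 8 (AST or ALT at or above 1.5 times the upper limit of normal) miss a patient with normal liver tests and no known liver disease.
- Exclusion 9 ("Any clinically significant laboratory abnormality that would affect interpretation of study data", or safety) and exclusion 11 ("clinically important history of a medical disorder that would compromise patient safety or data quality") can be used to exclude, but both depend on the investigator's judgment.

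**Step 5: what limits harm if such a patient is dosed?** Table 1 has chemistry at every visit. Section 3.1 has the sponsor's medical monitor and safety physician review each patient's safety data at Day 28. Section 4.4.1 has aminotransferase stopping rules as well as the reactivation rule. Appendix 1 repeats surface antigen in the liver work-up, where a newly positive result would point to reactivation.

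**Step 6: does the proposed wording remove the conflict?** With core antibody negative required for the exemption, the patient in step 3 no longer meets it. With a positive surface antigen or core antibody stated to count as hepatitis B positive, steps 1 and 2 rest on text and not on inference. Both deciding markers are already drawn.

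**The case against.** The strongest reply is that the criterion works as it stands. A positive result on a test listed for screening is most naturally a positive for that virus, and the exemption speaks of vaccination, so a site holding a positive core result has no good reason to apply it. Section 3.1 also requires all screening results to be available when eligibility is reconfirmed before randomization. Most of this stands. It means that a reader who infers that the protocol leaves every core-antibody-positive patient undecided, or that it sets out to admit them, goes further than the text supports. It does not remove the conflict in step 3, because the definition of vaccination expressly fits that patient.

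A second reply concerns the comparison with tuberculosis. There the protocol is explicit: it excludes "History or evidence of active or latent tuberculosis", and section 5.1.3 adds that "if the repeat test is positive or indeterminate, the patient will be excluded from the study". That shows that the protocol can state such a rule, but it carries little weight. Section 5.1.3 deals largely with indeterminate results of one assay, and HIV and hepatitis C have no result-handling text either.

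A third reply is that part of the record is not available. Several Table 1 footnotes cannot be read, and the laboratory manual and safety management plan are separate documents. An operating rule may exist there. That limits any claim that sites would actually differ. It does not affect the wording of criterion 7, which is fully visible.

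**Conclusion.** The point holds in a narrow form. The vaccination exemption in criterion 7 is defined so that it also fits a resolved infection, and read literally it admits a patient at risk of an event that the protocol itself lists as a reason to stop drug. This happens only when a surface antibody result is available from outside the listed panel and a site follows the parenthesis over the natural reading of the first sentence. Judgment-based exclusions before dosing and monitoring afterwards limit the consequences. Severity is minor; this is a cheap improvement, not a design fault.

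A reader might want to put a number on the patients affected. The documents do not support one: they give no core antibody prevalence, no number screened, and nothing on how sites would read the exemption. No endpoint, analysis or error rate is shown to change.

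The conclusion rests on two assumptions: the usual serological meaning of the three markers, and that no unseen operating document already states the rule.

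**What to change.** In criterion 7, in both the Protocol Summary and section 4.2:

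- Limit the vaccination exemption to *surface antibody present, with surface antigen and core antibody both negative*.
- State that *a positive surface antigen or a positive core antibody counts as positive for hepatitis B*.

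The cost is one clause in each of two places, made by amendment under section 12. No new assay is needed, since section 5.1.4 already draws both deciding markers. Surface antibody need not be added to the panel, because eligibility would then turn on the two markers that are there. The downside is that the few core-antibody-positive patients become clearly ineligible.

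If the sponsor would prefer to admit such patients, the alternative is a negative viral DNA test at entry with repeat testing on treatment. That needs an assay and monitoring not on the visible schedule, so exclusion is simpler for a 12-week trial of about 25 patients.
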